Appendix 2 Summary of Efficacy Analyses

Appendix 3 Adverse Event and Prior/Concomitant Medication Date Imputations

Adverse Event Start/Stop Date Imputation

Parameter	Missing	Additional Conditions	Imputation
Start date	D	M and Y same as M and Y of first dose of study drug	Date of first dose of study drug
for AEs	D	M and/or Y not same as date of first dose of study drug	First day of month
		Y same as Y of first dose of study drug	Date of first dose of study drug
	D and M	Y prior to Y of first dose of study drug but same as Y of screening date	Date of screening date
	D, M, Y	None - date completely missing	Date of first dose of study drug
Stop date	D	M and Y same as M and Y of last dose of study drug	Date of last dose of study drug
for AEs	D	M and/or Y not same as date of last dose of study drug	Use last day of month
	D and M	Y same as Y of last dose of study drug	Date of last dose of study drug
		Y not same as Y of last dose of study drug	Use Dec 31
	D, M, Y	None - date completely missing	No imputation, but assume ongoing

Imputation Rules for Partial Dates (D = day, M = month, Y = year)

Note: In all cases, if an estimated start date is after a complete stop date, use the first day of the stop date month. Similarly, if the estimated stop date is before a complete or imputed start date, use the last day of the start day month. In all cases, if it cannot be determined if the adverse event occurred prior to or after the first dose of test article, the adverse event should be defined as treatment emergent.

Prior and Concomitant Medication Start Date Imputation

Parameter	Type of Medication	Imputation
Start date for con meds	Non- Antibacterial	If it cannot be determined whether or not the start date of a medication (non-antibacterial) is prior to the first dose of study drug, it will be assumed that the medication was received prior to the first dose of study drug.
	Antibacterial	Missing start dates for antibacterials will be queried for a value. If it cannot be determined whether or not the start date of an antibacterial is prior to the first dose of study drug, it will be assumed that the medication was received prior to the first dose of study drug unless the indication notes that the medication was received after the first dose of study drug.
Stop date for con meds	Non- Antibacterial	If it cannot be determined whether or not the stop date of a medication (nonantibacterial) is after the first dose of study drug, it will be assumed that the medication was received after the first dose of study drug
	Antibacterial	Missing stop dates for antibacterials will be queried for a value. If it cannot be determined whether or not the stop date of an antibacterial is after the first dose of study drug, it will be assumed that the medication was received after the first dose of study drug unless the indication notes that the medication was received prior to the first dose of study drug. If it cannot be determined whether the antibacterial was received prior to the assessment of Early Clinical Response, the EOT and/or the PTE Visit, the antibacterial will be assumed to have been received through the PTE Visit.

Laboratory Test	Parameter	Worst Value
Hematology	Hematocrit	Lowest value
	Red blood cell count	Lowest value
	Mean corpuscular hemoglobin	Lowest value
	Mean corpuscular hemoglobin concentration	Lowest value
	Hemoglobin	Lowest value
	Mean corpuscular volume	Lowest value
	White blood cell count	Lowest value
	Platelets	Lowest value
	Eosinophils/Differential	Highest Value
	Neutrophils	Lowest Value
Chemistry		
	Alkaline phosphatase (ALP)	Highest value
	Alanine aminotransferase (ALT)	Highest value
	Aspartate aminotransferase (AST)	Highest value
	Bicarbonate	Lowest value
	Blood glucose	Both highest value and lowest value
	Blood urea nitrogen	Highest value
	Calcium	Both highest value and lowest value
	Chloride	Both highest value and lowest value
	Creatinine	Highest value
	Creatine phosphokinase (CK)	Highest value
	Gamma-glutamyl transpeptidase (GGT)	Highest value
	Lipase	Highest value
	Magnesium	Both highest value and lowest value
	Phosphorus	Both highest value and lowest value
	Potassium	Both highest value and lowest value
	Sodium	Both highest value and lowest value
	Total bilirubin	Highest value
Coagulation	Prothrombin time international normalized ratio (INR)	Highest value

Appendix 4 Directionality of Worst Laboratory Parameters

Appendix 5 Modified Division of Microbiology and Infectious Diseases Adult Toxicity Table

The DMID Adult Toxicity Table (21-NOV-2007) was modified to exclude the clinical component of the toxicity grading because clinical signs and symptoms related to abnormal laboratory values are not collected in this study. In addition, Grade 0 was added to the table so that shifts from normal could be analyzed. Grades for enzymes were modified as indicated in the table below.

For toxicity grades based on a multiple of the ULN, the normal range from the central laboratory will be applied.

For toxicity grades based on fixed values, the grades will be assigned regardless of the normal actual range values from the central laboratory. For example, a hemoglobin value of 10.0 gm/dL will be assigned a grade of 1 toxicity, even if the lower limit of normal from the laboratory was 9.8 gm/dL.

	HEMATOLOGY										
	Grade 0	Grade 1	Grade 2	Grade 3	Grade 4						
Hemoglobin (gm/dL)	> 10.5	9.5-10.5	8.0-9.4	6.5-7.9	< 6.5						
Absolute Neutrophil Count (count/mm ³)	> 1500	1000-1500	750-999	500-749	< 500						
Platelets (count/mm ³)	\geq 100,000	75,000-99,999	50,000-74,999	20,000-49,999	< 20,000						
WBCs (count/mm ³)	1000-10,999	11,000-12,999	13,000-14,999	15,000-30,000	> 30,000 or < 1,000						

	CHEMISTRY								
	Grade 0	Grade 1	Grade 2	Grade 3	Grade 4				
Hyponatremia (mEq/L)	> 135	130-135	123-129	116-122	< 116				
Hypernatremia (mEq/L)	< 146	146-150	151-157	158-165	> 165				
Hypokalemia (mEq/L)	> 3.4	3.0-3.4	2.5-2.9	2.0-2.4	< 2.0				
Hyperkalemia (mEq/L)	< 5.6	5.6-6.0	6.1-6.5	6.6-7.0	> 7.0				
Hypoglycemia (mg/dL)	≥ 65	55-64	40-54	30-39	< 30				
Hyperglycemia (mg/dL) (nonfasting and regardless of prior history of diabetes)*	< 116	116-160	161-250	251-500	> 500				
Hypocalcemia (mg/dL) (corrected for albumin)	> 8.4	8.4-7.8	7.7-7.0	6.9-6.1	< 6.1				
Hypercalcemia (mg/dL) (correct for albumin)	≤ 10.5	10.6-11.5	11.6-12.5	12.6-13.5	> 13.5				
Hypomagnesemia (mEq/L)	> 1.4	1.4-1.2	1.1-0.9	0.8-0.6	< 0.6				
Hypophosphatemia (mg/dL)	≥ 2.5	2.0-2.4	1.5-1.9	1.0-1.4	< 1.0				
Hyperbilirubinemia (total bilirubin)	< 1.1×ULN	1.1-1.5×ULN	> 1.5- 2.5×ULN	>2.5-5×ULN	> 5×ULN				
Urea	< 1.25×ULN	1.25-2.5×ULN	> 2.5-5×ULN	> 5-10×ULN	>10×ULN				
Hyperuricemia (uric acid) (mg/dL)	< 7.5	7.5–10.0	10.1–12.0	12.1–15.0	> 15.0				
Creatinine	< 1.1×ULN	1.1-1.5×ULN	> 1.5- 3.0×ULN	> 3.0-6×ULN	>6×ULN				

*The DMID toxicity table reports hyperglycemia detected in nonfasting specimens obtained from subjects with no prior diabetes.

	ENZYMES										
	Grade 0	Grade 1	Grade 2	Grade 3	Grade 4						
AST (SGOT)	< 1.25×ULN	1.25-2.5×ULN	> 2.5-5×ULN	> 5-10×ULN	>10×ULN						
ALT (SGPT)	< 1.25×ULN	1.25-2.5×ULN	> 2.5-5×ULN	> 5-10×ULN	> 10×ULN						
GGT	< 1.25×ULN	1.25-2.5×ULN	> 2.5-5×ULN	> 5-10×ULN	> 10×ULN						
Alkaline Phosphatase	< 1.25×ULN	1.25-2.5×ULN	> 2.5-5×ULN	> 5-10×ULN	>10×ULN						
Amylase	< 1.1×ULN	1.1-1.5×ULN	> 1.5-2.0×ULN	> 2.0-5.0×ULN	> 5.0×ULN						
Lipase	<1.1×ULN	1.1-1.5×ULN	> 1.5-2.0×ULN	> 2.0-5.0×ULN	> 5.0×ULN						

Signature Page for PTK0796-CABP-19302 SAP V5.0 Final Clean (VV-CLIN-000293 v1.0)

Approval	Clinical
	29-May-2024 15:23:41 GMT+0000
Approval	
	Clinical 29-May-2024 15:25:06 GMT+0000
Approval	
	Preclinical 20 May 2024 15:22:50 CMT (0000
	29-May-2024 15:33:59 GMT+0000
A mmorrel	
Approval	Medical
	30-May-2024 14:31:32 GMT+0000
Approval	
	R&D Management
	30-May-2024 14:39:03 GMT+0000
Approval	Clinical
	05-Jun-2024 19:19:00 GMT+0000

Signature Page for PTK0796-CABP-19302 SAP V5.0 Final Clean (VV-CLIN-000293 v1.0)

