### **13.8** Pre-study Documentation

The investigator must provide the sponsor with the following documents before enrolling any subjects:

- Completed and signed Form FDA 1572 or equivalent.
- All applicable country-specific regulatory forms.
- Current signed and dated curricula vitae for the investigator, sub-investigators, and other individuals having significant investigator responsibility who are listed on the Form FDA 1572 or equivalent, or the clinical study information form.
- Copy of the IRB/IEC/REB approval letter for the protocol and informed consent. All advertising, recruitment, and other written information provided to the subject must be approved by the IRB/IEC/REB. Written assurance of continuing approval (at least annually) as well as a copy of the annual progress report submitted to the IRB/IEC/REB must also be provided to the sponsor.
- Copy of the IRB/IEC/REB-approved informed consent document to be used.
- Where applicable, a list of the IRB/IEC/REB members and their qualifications, and a description of the committee's working procedure.

- Copy of the protocol sign-off page signed by the investigator.
- Fully executed CSA.
- Where applicable, a financial disclosure form.
- A written document containing the name, location, certification number, and date of certification of the laboratories to be used for laboratory assays and those of other facilities conducting tests. This document should be returned along with the statement of investigator form. The sponsor must be notified if the laboratory is changed or if any additional laboratory is to be used.
- List of normal laboratory values and units of measure for all laboratory tests required by the protocol. This is required for each laboratory to be used during the study. The sponsor must be notified if normal values or units of measurement change.

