10.4 Laboratory Values

Summaries of laboratory data will include hematology, chemistry, and coagulation (INR only) parameters. Laboratory parameters will be presented in alphabetic order with the following exceptions: differentials of white blood cell (WBC) counts will be presented following the WBC results, and chemistry parameters will first be grouped by organ class (renal, liver, electrolytes, and other) and presented alphabetically within each of these classes, as shown below.

Organ Class	Laboratory Parameter
Renal	Blood urea nitrogen (BUN)
Renal	Creatinine
Liver	Alkaline phosphatase (ALP)
Liver	Alanine aminotransferase (ALT)
Liver	Aspartate aminotransferase (AST)
Liver	Total bilirubin
Liver	Gamma-glutamyl transpeptidase (GGT)
Electrolytes	Calcium (Ca)
Electrolytes	Carbon dioxide (CO ₂)
Electrolytes	Chloride (Cl)
Electrolytes	Magnesium (Mg)
Electrolytes	Phosphorus (P)
Electrolytes	Potassium (K)
Electrolytes	Sodium (Na)

Table 10.Laboratory Parameters and Organ Class

Organ Class	Laboratory Parameter
Other	Creatinine phosphokinase (CK)
Other	Lipase

Table 10.Laboratory Parameters and Organ Class

Baseline is defined as the central lab value closest to and prior to the first dose of study drug. If no central lab value is available prior to the first dose of study drug, the local lab value that is closest to and prior to the first dose of study drug will be used as baseline. For by visit analyses, central lab values will be used unless no central lab value was obtained in the visit window. In this case, local lab values will be used for the by visit analyses. All lab values (central and local) are used for determination of the overall worst post-baseline value.

Several analyses of the laboratory data will be presented. Descriptive statistics (based on International System units) for chemistry, hematology and coagulation values, and the change from baseline will be summarized by treatment group at each time point (ECR Visit, EOT Visit and PTE Visit), and for the overall worst value post-baseline (which includes unscheduled visits). Appendix 4 provides the directionality of the worst values for each laboratory parameter.

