Clinically notable laboratory values will be determined based on the modified Division of Microbiology and Infectious Diseases (DMID) criteria in Appendix 5. Shift tables will be presented to show the number of subjects with a laboratory value with a grade of 0, 1, 2, 3 or 4 at baseline versus the value at each visit and the worst post-baseline value. Number and percentage of subjects with at least a 2-grade increase from baseline (based on DMID criteria) will be summarized by treatment arm. Percentages for each laboratory test will be based on the number of subjects with a baseline and post-baseline evaluation of the specific laboratory test. A listing will be provided which gives all laboratory results for a given laboratory test for subjects who have at least one 2-grade increase from baseline.

The number and percentage (based on the number of subjects with a normal level at baseline) of subjects in each treatment group with an elevated transaminase level (> 3 × upper limit of normal [ULN], > 5×ULN, and > 10 × ULN), an elevated bilirubin level (> 1.5 × ULN and > 2 × ULN) will be presented by study visit. A listing of subjects who meet the laboratory criteria for Hy's law at the same visit will also be provided. The laboratory criteria for Hy's law is defined as 1) ALT or AST> 3 × ULN, ALP \leq 2.0 × ULN, and total bilirubin > 1.5 ULN and 2) ALT or AST> 3 × ULN, ALP \leq 2.0 × ULN, and total bilirubin > 2 × ULN.

Detailed subject listings of all laboratory data collected during the study (local and central laboratory data) will be provided, including calculated creatinine clearance (using the Cockcroft-Gault equation). Laboratory values outside normal limits will be identified in the subject data listings with flags for low (L) and high (H) as will laboratory values that meet the clinically notable thresholds (CN).

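### SAP Appendix 5 grades every ULN-multiple test on the central laboratory's range while SAP 10.4 admits local results, so local values can be misgraded where the two ULNs differ

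*SAP*

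**What the plan says.** The grading rule in SAP Appendix 5 is: "For toxicity grades based on a multiple of the ULN, the normal range from the central laboratory will be applied". It covers bilirubin, urea, creatinine, AST, ALT, GGT, ALP, amylase and lipase, and makes no exception for samples analysed elsewhere.

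SAP 10.4 lets local results into the graded data by three routes:

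- Baseline, as a fallback: "If no central lab value is available prior to the first dose of study drug, the local lab value" nearest to that dose takes its place.
- By visit, as a fallback when the window holds no central result: "In this case, local lab values will be used for the by visit analyses".
- Worst value, always: "All lab values (central and local) are used for determination of the overall worst post-baseline value".

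SAP 10.4 then applies the grades: "Clinically notable laboratory values will be determined based on the modified Division of Microbiology and Infectious Diseases (DMID) criteria in Appendix 5". The shift tables set the grade "at baseline versus the value at each visit and the worst post-baseline value", and "Number and percentage of subjects with at least a 2-grade increase from baseline (based on DMID criteria) will be summarized by treatment arm". A listing of subjects with such an increase follows.

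Two protocol passages bear on this. Section 8.12 assigns the safety analysis of specimens to the Central Laboratory. Section 13.8 asks each site for a "List of normal laboratory values and units of measure for all laboratory tests required by the protocol", for every laboratory used.

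**The concern.** The two SAP rules do not fit together. Appendix 5 reads as if every graded value were central, while 10.4 says that some are not. A local result can then be divided by the ULN of a laboratory that did not produce it.

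A grade shift is meant to show change in the patient. When one end of the comparison is central and the other local, it also carries the difference between the two laboratories' ranges. The error can go either way. A value that is unremarkable on its own range can be reported as a toxicity grade, and a true elevation can be graded too low. At stake are the by-arm grade tables for liver, kidney and pancreatic tests and the listing that follows from them.

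**Working it through.** The plan states no figure for this point. The one worked grade in Appendix 5 (haemoglobin 10.0 gm/dL, Grade 1) agrees with its table, which puts 9.5 to 10.5 in Grade 1.

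**Inputs.** The cutpoints come from Appendix 5. The documents give no ULNs, so r = local ULN / central ULN is an assumption, shown over a range.

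**Formula.** A local value at k times its own ULN is graded under Appendix 5 as k × r.

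**Spurious 2-grade difference from the range alone.** The value has to jump a whole grade band, so r must exceed the ratio of that band's limits. The narrowest band gives the lowest threshold.

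| Test | Lower limits of Grades 1 / 2 / 3 / 4 (× ULN) | Narrowest band | Overgrading needs r above | Undergrading needs r below |
|---|---|---|---|---|
| Lipase | 1.1 / 1.5 / 2.0 / 5.0 | 2.0/1.5 | 1.33 | 0.75 |
| Creatinine | 1.1 / 1.5 / 3.0 / 6 | 1.5/1.1 | 1.36 | 0.73 |
| Bilirubin | 1.1 / 1.5 / 2.5 / 5 | 1.5/1.1 | 1.36 | 0.73 |
| AST, ALT, GGT, ALP, urea | 1.25 / 2.5 / 5 / 10 | 2.5/1.25 | 2.0 | 0.5 |

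The last column is the inverse of the one before it. For lipase, 1.33 is the jump from Grade 1 to Grade 3; the jump from 0 to 2 needs 1.5/1.1 = 1.36.

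**Smaller ratios.**

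- At r = 1.0 no grade changes.
- A value at 1.05 × its own ULN is Grade 0 on that range. At r = 1.1 it reads 1.155: Grade 1 for creatinine, bilirubin and lipase, still Grade 0 for AST and ALT. At r = 1.25 it reads 1.3125, Grade 1 for AST and ALT too. At r = 1.5 it reads 1.575, Grade 2 for creatinine, bilirubin and lipase.
- A lipase at 2.0 × its own ULN (Grade 2) reads 2.2 at r = 1.1, Grade 3. A creatinine or bilirubin at 2.0 (Grade 2) reads 1.5 at r = 0.75, Grade 1.
- An ALT at 3.5 × its own ULN (Grade 2) reads 3.5 × 0.7 = 2.45 at r = 0.7, Grade 1.

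The table gives thresholds for the range acting alone. A one-grade artefact on top of a genuine one-grade rise also reaches the 2-grade count, so that count can be touched at smaller r.

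**Worst-value selection.** SAP Appendix 4 takes the highest raw value as worst for these tests. Suppose a subject has a central ALT at 2.5 × the central ULN (Grade 1) and the local ALT just described, which lies at 2.45 on the central scale but is Grade 2 on its own range. Raw selection picks the central result and reports Grade 1. Changing the ULN rule alone would not correct this.

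**After the change.** If each value is graded on the ULN of its own laboratory, k is graded as k and the artefact is zero for every r.

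**The case against.** The strongest defence is that a single central range may be a deliberate common yardstick. It keeps every local value in the tables and applies identically in both arms. Scheduled chemistry (Screening, ECR, EOT and PTE) is central, and local results are only a fallback in two of the three routes. The outputs are descriptive, with no test or decision rule attached, and allocation is randomised 1:1.

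Much of this stands, and it rules out several stronger readings that a reader might infer:

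- *That local values are misgraded as a matter of course.* A grade changes only if the ULNs differ and the value lies near enough to a cutpoint.
- *That unscheduled post-baseline values are normally local.* Protocol 8.21.4 says only that further results from routine care may exist. Their number, and how often they set the worst value, is not given.
- *That lipase, with the lowest threshold, is the main exposure.* The local screening minimum in SAP Appendix 1 includes transaminases and bilirubin but not lipase. For transaminases the 2-grade threshold is r above 2.0.
- *That a treatment comparison is biased.* No direction between arms is shown.
- *That these are the main liver outputs.* SAP 10.4 also has separate transaminase, bilirubin and Hy's law summaries, which the Appendix 5 sentence does not govern because it concerns toxicity grades only.
- *That the local ULNs are ready to use.* Protocol 13.8 is a pre-study document request limited to protocol-required tests. It does not place the ranges in the analysis database.

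What does not stand is the defence by convention. The SAP neither states nor justifies one, and it is weakest for assay-dependent enzymes. Local testing is also real in this trial: Protocol 8.12 relies on it for eligibility, and SAP 8.2 computes creatinine clearance from local data.

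**Conclusion.** The conflict is real, and the rule is wrong as written for local values whose laboratory has a materially different ULN. Such values can be misgraded in either direction. The size cannot be computed, because it depends on two things the documents do not give: the ULNs, and how many graded values are local. The ratios in the table show what would be needed, with r as an assumption and each laboratory's own ULN taken as the right scale for its own results. The consequence is confined to descriptive laboratory safety tables and the 2-grade listing. Efficacy is untouched. The point deserves correction because the remedy is cheap, not because a distorted safety conclusion has been shown.

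**What to change.** 1. In SAP Appendix 5, apply to each ULN-multiple grade the ULN of the laboratory that produced the value, central or local, using the ranges requested under Protocol 13.8.
2. Where no local ULN is recorded, keep the value, grade it on the central ULN and flag it. Dropping it could remove a marked elevation from the worst-grade table.
3. For ULN-multiple tests, choose the worst post-baseline value by multiple of ULN, or by grade, instead of by raw value, and align Appendix 4 and SAP 10.4.
4. State the same ULN rule in SAP 10.4 for the transaminase and bilirubin thresholds and the Hy's law criteria, which name no laboratory's ULN at present.

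The cost is a few SAP sentences and a merge of local reference ranges into the analysis data. Some flagged values will still be graded on the central range, and their number should be reported by arm.
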